# 5.4 Participant Recruitment

Study participants will be recruited using a variety of methods including word-of-mouth, referral, advertising, and study announcement flyers posted in local treatment programs.

# 5.5 Number of CTP Sites

The trial will involve three community treatment programs (CTP).

#### 5.6 CTP Characteristics

Participating CTPs must:

- 1. Have a physician who can commit the time necessary to take a leadership role and oversee medical aspects of the study, perform medical assessments, confirm participant eligibility, prescribe study medications, administer study medications, review adverse events, and respond to adverse reactions that may occur during the course of the study.
- 2. Have at least one other medical clinician (i.e., physician, physician's assistant, or nurse practitioner) who can, in accordance with the regulations of the state where the site is located, make independent medical decisions and commit the time necessary to perform medical assessments, determine participant eligibility, prescribe study medications, administer study medications, review adverse events, and respond to adverse reactions that may occur during the course of the study.
- 3. Have a standard operating procedure in place for handling medical and psychiatric emergencies.
- 4. Have a physician available to provide after-hours clinical back-up for studyrelated emergencies.
- 5. Have access to a phlebotomist or other appropriately qualified medical personnel to complete blood draws.
- 6. Have access to, or the ability to contract with, a pharmacy/pharmacist (or other appropriate licensed entity) to store/dispense study medications as directed by the protocol, in accord with local regulations and NIDA stipulations.
- 7. Have adequate facility space available that will enable the performance of study procedures.

#### 5.7 Rationale for CTP Selection

The three sites selected for participation in this trial were selected, in part, based on the node's interest in participating in the trial, and the presence of an existing team of experienced personnel knowledgeable in clinical trial operations and trained in core CTN assessments at the site. Information on site readiness and capacity gathered via a survey sent to Node Principal Investigators confirmed the following.

- An ability to recruit and enroll a minimum of 2.5 methamphetamine dependent individuals (not currently in treatment) each month over a rapid recruitment period.
- Experienced regulatory personnel capable of timely preparation of necessary regulatory documents and the ability to facilitate an expeditious IRB submission, approval, and continuing review process.
- Medical staff who could commit the time necessary to oversee medical aspects of the study, perform medical assessments, confirm participant eligibility, prescribe and administer study medications, and respond to possible adverse reactions that may occur during the course of the study.
- Familiarity with Electronic Data Capture systems and the capacity and discipline to conform to protocol-required direct data entry procedures.

• Adequate and available space that is appropriately fitted to enable the performance of study procedures.

# 6.0 OUTCOME MEASURES

#### 6.1 Primary Efficacy Outcome Measure

The primary efficacy outcome measure is MA-negative urine drug screen (UDS) test results over the course of twice-weekly visits in the final four weeks of the active medication phase. Participants who provide at least 6 of 8 MA-negative UDS tests during the evaluation period, including a MA-negative UDS test at the last clinic visit in the last week of the active medication phase, will be defined as "responders." To determine the efficacy of XR-NTX+BRP for reducing MA use, the primary endpoint will be the number of "responders" at the completion of the trial. Three or more responders at the end of Stage 1 and 9 or more responders at the end of Stage 2 will indicate that the medication combination has shown sufficient potential efficacy to warrant moving forward to a large-scale Phase II-III, placebo-controlled trial.

# 6.2 Primary Safety Outcome Measure

The safety and tolerability of the combination medication condition will be determined using participants' reports of adverse events and serious adverse events collected at clinic visits or via other contact.

#### 6.3 Secondary Outcome Measures

- Participant-reported acceptance of protocol medications and procedures will be measured by satisfaction scales.
- · Craving and psychological measures will be collected weekly.
- Data on other measures of interest will also be collected, including the success of cellphone based procedures and other measures to enhance medication adherence and adherence to other study procedures.

# 7.0 STUDY PROCEDURES

# 7.1 Screening and Baseline Phase

Assessments administered during screening will determine whether participants meet eligibility criteria and will provide baseline measures of drug use and other important life domains. Participants who do not successfully complete all screening items within 30 days of consent, including the naloxone challenge, will be considered screen fails.

# 7.1.1 Pre-screening Assessment

Individuals responding to recruitment materials or otherwise referred to the study will be prescreened on the phone or in person to ascertain preliminary eligibility status. A series of questions (e.g., presence of MA use history, interest in participating in research to investigate medications that have potential to reduce MA use, ability and willingness to participate for the duration of the trial, etc.) will determine preliminary eligibility. Full screening appointments will be scheduled for those who meet preliminary eligibility criteria.

# 7.1.2 Informed Consent

At the start of the screening appointment before any assessments are administered, qualified study personnel will conduct the consent interview with prospective participants. The consent interview will include a description of the study, including study procedures and study medications. Participants will be given a copy of the IRB-approved consent form to review either on site or at home in accordance with requirements of the local IRB. Participants who remain interested after review of the consent form will be given a short quiz to ascertain their understanding of the project, its purpose, procedures involved, and the voluntary nature of participation. Those who do not successfully answer quiz items will have the study re-explained by research staff with a focus on aspects they did not understand. Anyone who cannot demonstrate appropriate understanding of the study will be ineligible to participate and will be assisted in finding other treatment resources if desired. Those who demonstrate understanding of the study and who voluntarily agree to participate will be asked to sign the informed consent form and proceed with screening assessments.

# 7.1.3 Screening Assessments

Upon signing the informed consent, participants enter a maximum 30-day screening phase to complete assessments to determine eligibility and to collect baseline data. Eligible participants must meet DSM-5 criteria for severe stimulant use disorder (methamphetamine type).

During the screening phase, prospective participants must submit at least three urine samples positive for methamphetamine out of a possible four tests to occur within a 14-day period during which clinic visits occur with at least two days between visits. In addition, participants must self-report MA use on 20 or more days in the 30-day period prior to consent using the Timeline Follow-Back. These criteria will be used to confirm current MA use and further substantiate a diagnosis of severe methamphetamine use disorder.

Once the participant completes all screening and baseline assessments, submits three MApositive UDS tests, and is found otherwise eligible for continued participation, he/she may begin the pre-induction procedure (see below). Participants who do not complete all screening assessments within the 30-day screening period or who are otherwise found to be ineligible for participation in the study will be considered screen fails. Participants who fail screen will not be allowed to return at a later date to repeat the screening process. Section 8.0 describes all study assessments.

#### 7.1.4 **Pre-Induction Strategy**

The screening/baseline phase includes a pre-induction procedure to be conducted after all other eligibility criteria have been met. The pre-induction strategy is designed to ensure participants meet subjective and objective measures of being opioid-free, per study medical clinician's determination, prior to enrollment and medication induction. The bullets below outline steps for determining final eligibility of all study participants.

- Participants must self-report no clinically significant opioid use (i.e., at any level that could constitute a potential risk of precipitating opioid withdrawal upon naloxone administration) in the seven days prior to the naloxone challenge, as measured using the Timeline Follow-Back and by the Prior and Concomitant Medication assessment.
- To confirm opioid abstinence, a UDS administered on the day of the naloxone challenge must be negative for opioids prior to administration of the challenge. Individuals who are opioid-negative will continue in the pre-induction process. Individuals may provide an additional urine drug screen on a subsequent day if the study medical clinician determines that a second screen is appropriate.
- The naloxone challenge will be administered prior to study medication induction. A minimum 0.8mg bolus must be given before determining the outcome of the challenge. The study medical clinican will determine whether the participant is eligible to continue on to XR-NTX induction based on clinical judgment. Evidence of withdrawal signs or symptoms following naloxone administration will result in postponement of XR-NTX administration until a negative challenge result is achieved.

Participants who experience withdrawal symptoms following the naloxone challenge may be treated with ancillary medications, observed until symptoms resolve, and given the opportunity to return another day and be re-challenged if clinically indicated. Participants who are not interested in continuing to participate, or who fail a repeat naloxone challenge, will not be eligible to participate in the study but will be given referrals to local treatment programs as appropriate.

#### 7.1.5 Final Determination of Eligibility and Enrollment

After completing all screening assessments including the naloxone challenge, the study physician must review and approve safety and eligibility assessments in order to confirm participant eligibility prior to enrollment. Enrollment will occur on the same day following the successful naloxone challenge after study eligibility has been confirmed and documented. The enrollment procedure will be conducted in a centralized process through the CTN Data and Statistics Center (DSC).

#### 7.2 Active Medication Phase

#### 7.2.1 Intervention

#### 7.2.1.1 Pharmacotherapy

**Extended-release Depot Naltrexone (XR-NTX).** Participants will receive the first XR-NTX injection on the day of enrollment, following a successful naloxone challenge and confirmation of study eligibility. The second injection of XR-NTX will be administered at the beginning of Week 5. Prior to the second XR-NTX administration, a naloxone challenge may be administered again at the discretion of the study medical clinician to ensure continued suitability for XR-NTX. The XR-NTX injection shall be administered following guidelines in the package insert.

Well-developed precautionary procedures will be followed to avoid adverse events associated with medication administration. For example, body habitus will be assessed during the physical exam at screening to assure that intramuscular administration is feasible as an inadvertent subcutaneous injection of XR-NTX may increase the likelihood of injection site reactions. Individuals whose body habitus precludes a gluteal intramuscular injection of naltrexone using the needles provided will be excluded from the study.

**Extended-Release Bupropion (BRP).** The first dose of BRP will be given on the day of enrollment (Day 1) immediately following XR-NTX administration. Take-home oral study medication (BRP) will be dispensed weekly for dosing on non-clinic days. Participants will be asked to bring their BRP medication bottle to the clinic for each visit so that self-administration of the BRP dose for each in-clinic visit day can be observed by medical staff. A daily dose of 150 mg will be dispensed for Days 1 and 2, 300 mg daily for Days 3 and 4, and 450 mg daily for Days 5 through 56. If the participant reports intolerable symptoms or side effects at the full 450 mg BRP dose, and it is deemed appropriate by the study medical clinician, a dose reduction may occur. The dose may be reduced to 300 mg daily. If intolerable adverse effects continue, the participant may be withdrawn from further medication administration. If intolerable adverse effects resolve after an initial dose reduction, and it is deemed appropriate by the study medical clinician, and the study medical clinician, titration to the full 450 mg target BRP dose may be attempted again up to Day 21.

#### 7.2.1.2 Medical Management

At each clinic visit, participants will meet with a study medical clinician to discuss adverse events, consider potential medication side effects, and discuss other pertinent issues in keeping with sound medical practice. Ancillary medications may be provided for study medication-related adverse events as clinically indicated. A range of prescription and over-the counter ancillary medications may be used for anxiety, nausea, vomiting, diarrhea, muscle pain, and insomnia. At all medical management visits, the medical clinician will remind participants about the importance of adhering to the study procedures, including attending scheduled clinic visits and complying with cellphone-based dosing confirmation procedures.

#### 7.2.1.3 Medication Adherence Procedures

To improve adherence to the bupropion dosing regimen and other protocol activities (e.g., clinic attendance), the protocol includes a cellphone component designed to increase and document daily dosing adherence.

**Technology Training.** After eligibility has been established and the participant has been enrolled in the active medication phase of the study, staff will provide instruction on the use of the study-provided cellphone to enhance and document adherence with medication taking.

**Cellphone Equipment.** Participants will be provided with a study cellphone (and battery charger). Phones will be camera-equipped and capable of e-mail, text messaging, voicemail, still photo and video recording. Airtime/service plans will be included, to allow participants to make personal calls and send text messages without restriction. The cellphone equipment will be retained by participants through the end of their participation in the study. If the participant does not require a replacement cellphone during the course of the study, the participant will have the option to keep the study cellphone. Airtime/service plans will not be provided beyond the end of participation in the study. Replacement cellphones and cellphones participants chose not to keep should be returned at the end of study participation.

**Cellphone-based Procedures.** Prior to enrollment, study personnel will request a signed agreement from participants regarding the use of the cellphone for the purposes of the study. Participants will be informed of the medication adherence procedures, including the requirement to record videos of oral study medication ingestion at home. If a participant fails to bring his/her oral study medication to the clinic so that self-administration of the dose can be observed, the participant will be asked to record a video of him/herself taking the dose for that day at home (if the dose has not already been taken). If the participant records the video, he/she will be compensated as if the medication bottle was returned to the clinic that day for in-clinic observed dosing. Because the purpose of providing study cell-phones is to document medication dosing on non-clinic days, participants will be informed of and trained on video recording and transfer procedures (including practice sessions in clinic; details in MobiControl Video Instructions SOP.)

**Set-up and Maintenance of Cellphone Equipment.** IT staff will prepare the phones, preprogram the cellphone number, and install required applications including the Device Management System (i.e., MobiControl) used to securely store and transmit the recorded dosing videos. IT staff will work with clinical and research staff to ensure proper use of phones and to resolve problems and replace equipment as needed in a timely manner.

**Lost/Stolen/Inoperable Cellphones.** Participants will be notified that failure to maintain the phone in their possession will result in a "lost or stolen phone" report to the service provider, disabling the SIM card, deleting the contents, and nullifying the service on the phone, thus rendering the cellphone useless and of limited value. Tracking programs installed on study cellphones will only be accessed upon report of a lost/stolen phone. Study staff will not use the cellphone tracking application to track or locate participants. A one-time replacement of a lost, stolen, or inoperable study-provided phone may be permitted. A second loss/theft of a study phone will not be replaced.

**Protection of Participant Privacy Regarding Cellphone.** At no time will the study personnel access the cellphone-based memory of usage in terms of time, numbers called, text messages received or sent, or web browsing history, unless requested by the participant to help troubleshoot a problem. Additionally, the tracking program will be accessed only in the case of a lost/stolen phone. Access to the phones is restricted to the study personnel who are directly involved in the trial. Participants will be advised on how to secure their phones with passwords and how the mobile device management application (i.e., MobiControl) will be used to transmit

dosing video to the study team as an encrypted file. Participants will be advised to delete video recordings on the cellphone upon staff confirmation of successful transmission.

**Staff-to-Participant Cellphone Contact.** Staff will make calls and/or send texts or e-mails as regular reminders for clinic visits or dosing requirements. If a participant has not recorded the dosing video by an agreed upon time on a take-home dosing day, study staff will contact the participant to ask the participant to take his/her study drug dose and document it via cellphone-recorded video as soon as possible.

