# 2.2 Study Design

Stage 1 will include 20 individuals with severe stimulant use disorder (methamphetamine type) enrolled across three study sites. Following a maximum 30-day screening period to establish eligibility, participants will receive a monthly injection of extended-release depot naltrexone (XR-NTX; as Vivitrol®) plus once-daily bupropion extended-release tablets (BRP; as Wellbutrin XL®) for 8 weeks. Take-home oral study medication (BRP) will be dispensed weekly for dosing on non-clinic days. Participants will be asked to attend clinic twice weekly for observed BRP dosing, collection of urine samples, assessments, and medical management. Following the 8-week active medication phase, participants will complete a follow-up phase, including a medication taper and post-medication phase follow-up visit during Week 9. If Stage 1 data document success (see criteria below) in at least 3 "responder" study participants, Stage 2 will follow utilizing the same protocol as in Stage 1, to enroll an additional group of 29 participants. Using the same criteria of "responder" success, if the combined stages document success in at least 9 of 49 study participants, the combination medication will be considered to have shown sufficient potential to advance to a large-scale placebo-controlled trial.

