#### 7.2.2.3 Lost Medication

There will be no replacement of any dispensed study medications.

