#### 7.2.2.4 Prescribing and Dispensing Study Medications

All study medications shall be prescribed and dispensed by delegated medical staff licensed and appropriately trained to prescribe and dispense study medications. XR-NTX injections will be administered during Week 1, and again at the first visit of Week 5. Oral BRP will be provided to the participant weekly in labeled medication bottles that will include both in-clinic, observed doses and self-administered doses for non-clinic days.

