# 8.4.3 BRP Observed Dosing

Oral study medication (BRP) will be dispensed for take-home weekly. Participants will be asked to bring his/her BRP medication to the clinic for each visit so that self-administration of BRP dose for each in-clinic visit day can be observed by medical staff. If a participant fails to bring his/her oral study medication to the clinic so that self-administration of the dose for the in-clinic visit day can be observed, the participant will be asked to provide a video recording of themselves taking the dose for that day at home. If the participant records the video, h/she will be compensated as if the medication bottle was returned to the clinic that day.

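### When a take-home dosing video is missing, staff ask the participant to take and film the dose without first asking whether it was already taken

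*Protocol*

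**What the plan says.** The reminder rule is in Section 7.2.1.3, under staff-to-participant cellphone contact. Its trigger is "If a participant has not recorded the dosing video by an agreed upon time on a take-home dosing day". Its action is that "study staff will contact the participant to ask the participant to take his/her study drug dose and document it via cellphone-recorded video", promptly. It has no branch for a dose that was swallowed but not filmed.

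Earlier in the same section, the rule for a clinic day on which the bottle was not brought is worded differently. The participant is then "asked to record a video of him/herself taking the dose for that day at home (if the dose has not already been taken". Section 8.4.3 restates that clinic-day rule without the condition: "the participant will be asked to provide a video recording of themselves taking the dose for that day at home".

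The regimen is "once-daily bupropion extended-release tablets", titrated from 150 mg on Days 1 and 2 to "300 mg daily for Days 3 and 4, and 450 mg daily for Days 5 through 56" (Section 7.2.1.1), with a possible reduction to 300 mg. Tablets are supplied in weekly bottles "that will include both in-clinic, observed doses and self-administered doses for non-clinic days" (Section 7.2.2.4). Section 7.2.2.3 adds: "There will be no replacement of any dispensed study medications".

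**The concern.** The reminder rule treats the absence of a video as the absence of a dose. A participant may have taken the tablets and forgotten to film. Section 8.4.5 logs the recordings that staff receive, so a dose that was filmed but failed to transfer could also look like a missing video. Read literally, the instruction then asks that participant to take a dose.

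Several features make a literal response possible:

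- The weekly bottle holds further tablets.
- Section 7.4 pays $10 for a take-home dose only if it is video-confirmed, and Section 10.5 counts only doses confirmed by video or in clinic. Both favour filming a dose over reporting one already taken.
- Staff reminders may go by call, text or e-mail. If this contact is made in writing, there may be no conversation in which the earlier dose comes up.
- Dose Logs (Section 8.4.4) record self-reported doses but are completed at visits, so they could reveal a repeat only afterwards.

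What is at stake is safety. Section 11.24.1 calls seizure the most serious reported side effect of bupropion, ties minimised risk to a daily total of no more than 450 mg, and lists stimulant addiction among the circumstances that raise the risk. Every enrolled participant has severe methamphetamine use disorder, and the target dose already sits at 450 mg, so there is no margin.

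**Working it through.** The plan gives no figure of its own on this point. The check compares the two rules and then works out what a repeat dose would mean.

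**The two rules in Section 7.2.1.3**

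| | Clinic day, bottle not brought | Take-home day, no video |
|---|---|---|
| Trigger | Bottle missing | Video missing |
| Request | Film the dose at home | Take the dose and film it |
| Already-taken condition | Stated | Not stated |
| Clinician seen that day | Yes (Section 7.2.1.2) | No scheduled visit |

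The authors recognised the already-taken case, but stated it only for the less common pathway. Take-home days are the routine one: 5 × 8 = 40 videos in the active phase plus 4 during the taper, 44 in all (Section 7.4, Table 1). No other section extends the condition to those days.

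**Daily total if an unfilmed dose is repeated once**

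Formula: 2 × scheduled daily dose, compared with the 450 mg in Section 11.24.1.

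| Scheduled dose | Total with one repeat | Against 450 mg |
|---|---|---|
| 450 mg (Days 5–56) | 2 × 450 = 900 mg | 450 mg over; 900/450 = 2.0 times |
| 300 mg (Days 3–4, or reduced dose) | 2 × 300 = 600 mg | 150 mg over; 600/450 = 1.33 times |
| 150 mg (Days 1–2) | 2 × 150 = 300 mg | not over |

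With the already-taken condition in place, a participant who follows the reminder takes at most the scheduled dose.

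**Seizure risk.** Appendix B gives 1 in 1000 at 450 mg daily. The document gives no rate for a higher daily total and no frequency for unfilmed doses, so the added risk cannot be computed.

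**Effect of the correction on adherence counts.** Days 1–56 give 56 daily doses. The threshold in Section 10.5 is 0.80 × 56 = 44.8, so 45 confirmed doses are needed: 45/56 = 80.4%, whereas 44/56 = 78.6%. A participant may therefore have 56 − 45 = 11 unconfirmed doses and still qualify. Each one lowers confirmed adherence by 1/56 = 1.8 percentage points.

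**Effect on payment.** One forgone video costs $10 of a possible 44 × $10 = $440, or 2.3%.

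**The case against.** The strongest reply is that nothing in the protocol orders a second dose. The regimen is once daily, and the reminder refers to the participant's dose in the singular, so someone who has already dosed has none outstanding and would probably say so. The text is silent on asking first; it does not forbid it. The Operations Manual (Section 12.1) is meant to carry day-to-day detail, Section 7.2.1.3 cites an SOP for video recording and transfer, and Section 9.0 requires training. Any of these may contain the check. Participants see a clinician twice weekly, are asked to bring the bottle to each visit, and dispensed and returned medication is accounted for. The payment motive is also weaker than it looks. If the bottle holds exactly one week's doses, a repeat leaves a later day short, and if that is a take-home day its $10 is lost and the net gain is nil.

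Most of this stands, but it bears on how likely a repeat is. The visit-based checks and the tablet shortage would help detect a repeat or discourage another; they do not stop the first. A check in a document that is not shown cannot be assumed, and it would not correct an unconditional instruction in the protocol. The singular wording helps a careful reader, yet the same section spells out the condition where it was thought to matter. The omission in Section 8.4.3 is clerical only, because Section 7.2.1.3 states the condition for that situation and the participant sees a clinician that day.

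**Conclusion.** The concern holds. For take-home days the protocol gives an operative dosing instruction triggered by a missing video alone, with no step for a dose already taken. Followed literally by a participant who had dosed without filming, it produces 900 mg at the 450 mg dose or 600 mg at the 300 mg dose, against the 450 mg daily total linked to minimised seizure risk.

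These totals assume one full repeat on the day of contact. They are not estimates of frequency: how often doses go unfilmed, and how often a participant would repeat one, are unknown, and no event count is claimed. The further consequence that a later day would be left without tablets assumes that the bottle holds exactly that week's doses. The primary endpoint, sample size and error rates are untouched. The only analysis link is the secondary adherence-based analysis in Section 10.5. This is a safety gap that should be fixed because closing it costs almost nothing.

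**What to change.** Rewrite the reminder sentence in Section 7.2.1.3 so that staff contact the participant and first ask whether that day's bupropion has been taken.

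- If it has not, the participant is asked to take it and film it promptly, as now.
- If it has, staff tell the participant to take no more that day, and the dose goes on the Dose Log as self-reported and not video-confirmed.

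In Section 8.4.3, restore the already-taken condition that Section 7.2.1.3 states for the clinic-day rule.

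The cost is one sentence and one clause, plus matching text in the Operations Manual or SOP if either lacks it. A dose taken but unfilmed stays unconfirmed for the 80% adherence group, and the participant forgoes that day's video payment; the working above gives the size of both.
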